6.3.23 Mandatory pregnancy information collection period

Information on the occurrence of pregnancy must be collected throughout the clinical study, from the administration of the first dose of the investigational medicinal product until the completion of the CT.

6.3.24 The actions to be performed in case of pregnancy

The Investigator will collect information about the pregnancy of any female patient who became pregnant while taking part in this study. The Investigator will register pregnancy information and submit that information to the Sponsor. The procedure for pregnancy reporting is identical to the procedure for reporting a serious adverse event.

Pregnancy is not considered an AE; however, any complications of pregnancy or elective termination of pregnancy for medical indications will be documented as an AE. A spontaneous abortion is always considered an AE and shall also be reported to the Sponsor. Any patients who become pregnant will be withdrawn from the study. In addition to that, the Sponsor shall be notified of any AE resulting from a pregnancy that occurred after the end of study, if that AE is regarded by the Investigator as reasonably related to the IMP. Although the Investigator is not under an obligation to actively collect this information from former female study subjects, the Investigator may learn of the AE from spontaneous patient-reported outcomes.

7 EFFICACY ASSESSMENT

7.1 Efficacy parameters

Primary efficacy variable:

Occurrence of less than 1.0 case of infection/patient/year of a **serious bacterial infection**¹ during one year of treatment.

¹ **a serious bacterial infection** includes: sepsis; bacterial pneumonia; bacterial diseases of viscera (visceral abscess); bacterial meningitis; osteomyelitis/septic arthritis.

This variable is categorical, dichotomous, with categories of “sufficient efficacy” (occurrence of a **serious bacterial infection**¹ during the year of treatment, less than 1 case per year) / “insufficient efficacy” (occurrence of a **serious bacterial infection**¹ during the year of treatment, 1 or more cases per year). It will be assessed after the end of 52 weeks of treatment.

Secondary efficacy variables:

1. The threshold serum IgG level ≥ 5 g/L before the scheduled administration of the product (according to the PK study plan).

This variable is categorical, dichotomous, with categories of “response achieved” / “response not achieved”;

2. Cases of any non-serious infectious diseases during the treatment course, per patient per 1 year of therapy.

3. The duration of any non-serious infectious diseases during the treatment course, per patient per 1 year of therapy.

4. The fraction (%) of patients who were prescribed treatment with antibiotics.

5. The number of days of antibiotic therapy in a year (except for the cases where continuous antibiotic prophylaxis is performed).

6. Hospital admissions due to an infection (number of days and frequency in a year).

7. Fever episodes (number of events in a year).

8. The number of days of incapacity for work (sick leaves), or missing school/kindergarten due to an infection.

9. The quality of life level in the patients throughout the study period (data from questionnaires).

7.2 Assessment methods:

Subjects who withdrew during the screening phase are not counted in the efficacy and safety analysis since they have not received any administration of the investigational medicinal product (IMP).

The efficacy analysis counts only patients who have fully completed their participation in the study.

A detailed description of methods that are used for the efficacy assessment is given in Section 9.

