5.3 Subject exclusion criteria (discontinuation of treatment with the investigational product)

Table 5.3.1 – Exclusion criteria for CT subjects

No.	Exclusion criterion
1.	at the request of the patient/patient's parents/patient's legally authorised representative at any time and for any reason;
2.	patient developing serious and/or unexpected AEs/ARs during the study, which require discontinuation of the product;
3.	blood transfusions or transfusions of blood components and products, with the exception of the IMP;
4.	the need to use medicinal products disallowed as part of this study;
5.	systematic lack of patient compliance with the treatment regimen prescribed by the Investigator;
6.	systematic lack of patient compliance with the procedures specified in this protocol;
7.	exclusion based on screening results, including emergence of episodes of serious bacterial infections while receiving a previous IV immunoglobulin product and episodes of hospitalisation during the screening period (before the first administration of the IMP BP-SCIG 20%).

For all subjects withdrawn from the study due to AEs requiring discontinuation of treatment with the investigational medicinal product, it is required to conduct the final visit procedures as soon as possible after AE development. After discontinuation of treatment, the subject shall remain under observation until the reaction or its clinically significant signs disappear.

The reasons for leaving the study early must be documented in the eCRF.

Table 5.3.2. Criteria for exclusion of CT subjects from the investigation of PK parameters at the time of starting PK assessment

No.	Exclusion criterion
1.	Receiving the IMP BP-SCIG 20% for less than 4 months;
2.	Presence of episodes of serious bacterial infections (bacteraemia or sepsis, bacterial meningitis, osteomyelitis/septic arthritis, bacterial pneumonia, visceral abscess) at the time of investigation of PK parameters.

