9. STATISTICS

9.1. Contents of statistical analysis

Subjects who withdrew during the screening phase are not counted in the efficacy and safety analysis since they have not received any administration of the investigational medicinal product (IMP).

Subjects who have not received a full IMP course are included in the safety analysis, but are not included in the efficacy analysis.

Subjects who discontinued from the study after completing IMP administration during the follow-up period are included in the efficacy and safety analysis. The data of such subjects are evaluated by parameters that may be analysed at a certain time point. The dropped data are not analysed.

Subjects who received at least one dose of the IMP but withdrew from the study prematurely are included by the Investigator in the tolerability analysis of the investigational product.

Statistical analysis:

Populations for statistical analysis:

ITT (Intention-to-treat population) includes all study subjects who received the investigational product at least once. The data obtained from this sample will be used for the safety analysis.

PP (Per Protocol) includes all patients who complied with the protocol requirements. This population includes all patients who received full protocol therapy, who underwent all scheduled visits, and did not have significant protocol deviations. The data obtained from this sample will be used for analysis by efficacy criteria.

The main efficacy analysis is performed on the PP population, and the additional, confirmatory analysis is performed on the ITT population (all subjects who received ≥ 1 dose and who meet the inclusion criteria, and for whom efficacy can be established).

Plan of statistical analysis of CS results

Statistical analysis is performed by a qualified biostatistician, a third party contracted by the Sponsor. Statistical analysis includes the following:

- description of patients enrolled in the study;
- the number of drop-out subjects;
- the number of adverse events;
- efficacy analysis in the group;
- tolerability assessment in the group;
- safety assessment in the group;
- analysis of pharmacokinetic data;
- statistical inferences.

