9.11 Analysis dataset

ITT (Intention-to-treat population) includes all study subjects who received the investigational product at least once. The data obtained from this sample will be used for the safety analysis.

PP (Per Protocol) includes all patients who complied with the protocol requirements. This population includes all patients who received full protocol therapy, who underwent all scheduled visits, and did not have significant protocol deviations. The data obtained from this sample will be used for analysis by efficacy criteria.

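### The main efficacy analysis uses completers/per-protocol patients, so a serious bacterial infection that ends participation drops out of the rate being tested

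*Protocol*

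**What the plan says.** The primary efficacy question (sections 9.2, 9.4 and 9.10) is whether the SBI rate is below 1.0 per patient per year. The null hypothesis is rejected if the upper limit of the 99% confidence interval is below 1.0. The test is one-tailed, and section 9.8 sets its level at 0.01.

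Four statements decide who enters that test:

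- Section 7.2: "The efficacy analysis counts only patients who have fully completed their participation in the study".
- Section 9.1: "Subjects who have not received a full IMP course are included in the safety analysis, but are not included in the efficacy analysis".
- Section 9.1, further on: "The main efficacy analysis is performed on the PP population, and the additional, confirmatory analysis is performed on the ITT population". The ITT efficacy set is restricted to treated subjects who meet the inclusion criteria "and for whom efficacy can be established".
- Sections 9.1 and 9.11, on the per-protocol (PP) set: "This population includes all patients who received full protocol therapy, who underwent all scheduled visits, and did not have significant protocol deviations". Section 9.11 assigns PP to efficacy and ITT to safety, and does not mention an ITT efficacy analysis.

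For patients who leave late, section 9.1 says: "Subjects who discontinued from the study after completing IMP administration during the follow-up period are included in the efficacy and safety analysis".

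The on-treatment removal criteria in section 5.3 include "patient developing serious and/or unexpected AEs/ARs during the study, which require discontinuation of the product" and "the need to use medicinal products disallowed as part of this study". They also include transfusion of blood components or products and withdrawal at the patient's request.

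**The concern.** The endpoint is an event rate, and the rule for entering the main analysis depends on what happens to the patient after the first dose. An SBI is not itself a reason for removal in section 5.3. But sepsis, meningitis or a visceral abscess can lead to death, to a serious adverse event that ends treatment, to a blood product, to a disallowed medicine, to withdrawal, or to a missed visit. In each case the main analysis loses the patient, the SBI and the time already observed. Dropout unrelated to infection does not bias the rate. Dropout caused by an SBI can only lower it.

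Two things are at stake: the error rate of the primary test, on which section 9.10 also rests its non-inferiority conclusion, and the reported SBI rate, which is the main efficacy result.

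The statements also conflict. Section 9.1 both excludes patients with an incomplete course from efficacy and plans an ITT efficacy analysis that would include them. A patient who finishes the product but misses Visit 17 is in the efficacy analysis by one sentence of 9.1, and out of it by 7.2 and by the all-visits rule for PP. Two analysts could form different efficacy sets from the same data.

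**Working it through.** **The plan's own figure.** Sections 9.2 and 9.4 state that more than 40 patients give at least 80% power. No true SBI rate is assumed, so the figure cannot be reproduced directly. An exact one-sided Poisson test at 0.01 with 41 patient-years passes with at most 26 SBIs. Its power is 90.4% at a true rate of 0.5, 80.1% at 0.55 and 66.0% at 0.6. The claim is plausible if the true rate is about 0.55 or lower. The sample size is not the problem here.

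**Inputs from the protocol.** 56 patients enrolled (9.2), null rate λ = 1.0, level 0.01, decision by the upper 99% limit, 52 weeks of treatment (taken as one year).

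**Assumptions.** SBIs follow a Poisson process. A share q of SBIs leads to removal, and unrelated dropout is d = 10%. The protocol gives neither q nor d, so both are varied. It also does not say whether the 99% limit is one-sided (nominal 1%) or the upper end of a two-sided interval (nominal 0.5%), so both are shown.

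**Model.**

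- Probability that a patient completes: (1 − d) × exp(−λq).
- Number of completers: M ~ Binomial(56, (1 − d) × exp(−λq)).
- SBIs among completers: K ~ Poisson(M × λ × (1 − q)). Completers are by definition the patients with no SBI that led to removal, so their rate is λ(1 − q).
- Success: χ²(c; 2(K + 1)) / (2M) < 1.0, where χ²(c; ν) is the c-quantile on ν degrees of freedom, with c = 0.99 or 0.995.

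Worked entry, q = 20%: completion probability 0.9 × exp(−0.2) = 0.737, so 56 × 0.737 = 41.3 completers are expected, with a rate of 1.0 × 0.8 = 0.80.

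**Chance of declaring success when the true rate is 1.0** (completers by exact sums, all treated by simulation)

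| q | Expected completers | Rate in completers | Completers, one-sided 99% | Completers, two-sided 99% | All treated, person-time, one-sided |
|---|---|---|---|---|---|
| 0% | 50.4 | 1.00 | 0.8% | 0.4% | about 0.8% |
| 5% | 47.9 | 0.95 | 1.9% | 1.0% | about 0.8% |
| 10% | 45.6 | 0.90 | 4.0% | 2.3% | about 0.8% |
| 20% | 41.3 | 0.80 | 13.2% | 8.2% | about 0.8% |
| 30% | 37.3 | 0.70 | 30.4% | 21.8% | about 0.8% |

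With the two-sided limit, the all-treated analysis stays at about 0.4%. With the one-sided limit the level of 0.01 is already exceeded at q = 2% (1.1%).

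**Sensitivity to unrelated dropout** (one-sided limit). With d = 0% the result is 4.3% at q = 10% and 14.8% at q = 20%. With d = 20% it is 3.6% and 11.3%.

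**Information lost.** At λ = 1.0, q = 20% and d = 10%, all treated patients contribute 48.3 patient-years on average and completers 41.3. The main analysis discards 48.3 − 41.3 = 7.0 patient-years, together with the SBIs in them.

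**Lower true rates** (q = 20%, d = 10%, one-sided). A true rate of 0.5 is reported as 0.5 × 0.8 = 0.40, with a pass chance of 99% in completers against 95% in all treated. A true rate of 0.3 is reported as 0.24, with a pass chance of about 100% in both.

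**The case against.** The strongest objection is that the protocol already plans an ITT efficacy analysis and itself calls it confirmatory. The restriction to patients whose efficacy can be established can also be read favourably: a patient who left after an SBI has an established outcome (insufficient efficacy under 7.1), so only SBI-free early leavers would be lost. On that reading and with person-time as denominator, the false-positive risk stays below 0.5% (one-sided limit). But the protocol fixes neither the reading nor the denominator. Dividing the same events by head count gives roughly 1.1% to 4.1% for q = 10% to 30%. The ITT analysis is also additional to the PP analysis, and it is contradicted by 7.2, by another sentence of 9.1 and by 9.11. It reduces the problem without curing it.

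Second, the removal routes may be narrow. Section 6.2 allows antibiotics, an SBI is not an exclusion criterion, and section 5.3 removes only patients whose event requires discontinuation. Nothing in the protocol supports q of 20% or 30%. At a true rate of 1.0 and with no other dropout, those values mean about 10 or 15 of 56 patients lost to SBIs, which would be noticed. With d = 10%, q = 30% also leaves about 37 completers, below the 40 the plan requires. This stands: the upper rows of the table are extreme, and the rows at 5% and 10% are the more useful ones.

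Third, section 2.3 cites 0.04 severe infections per year. At that rate 56 × 0.04 = 2.24 SBIs are expected in a full year, the trial passes almost surely under either analysis, and q = 20% would change the reported rate only from 0.04 to 0.032. This also stands. It limits the practical harm but does not justify the choice of set.

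Fourth, the conflict over patients who leave during follow-up concerns one week and one visit after the 52-week assessment. It is minor, though it still needs a single rule.

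Lastly, the events are not lost to the trial altogether, since all treated patients remain in the safety analysis. They are lost to the main efficacy analysis.

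**Conclusion.** The concern holds and should be fixed. As written, the main SBI analysis conditions on completing the study, and any SBI that ends participation biases the rate downwards, in favour of success. At the null boundary, with 56 treated and 10% unrelated dropout, the one-sided error is 1.9% if 5% of SBIs lead to removal, 4.0% at 10% and 13.2% at 20%, against a stated 1%. These are scenarios, because the protocol supplies neither q nor a dropout rate, and they assume Poisson events. If the true rate is well below 1.0, the pass/fail decision is hardly affected and the cost is an understated SBI rate, by the factor 1 − q. The conflict between 7.2, 9.1 and 9.11 over who belongs in the efficacy analysis does not depend on any assumption.

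**What to change.** - **Primary analysis:** all patients with at least one dose of the investigational product. Total SBIs divided by total patient-years observed from first dose, with an exact Poisson upper limit. The protocol names no interval method; this one suits a rate with unequal follow-up. State whether the 99% limit is one-sided or two-sided.
- **Sensitivity analysis:** PP/completers.
- **Section 7.2:** remove the completers-only sentence.
- **Section 9.1:** remove the sentence excluding incomplete courses from efficacy, and the restriction to patients whose efficacy can be established. State one rule for patients who leave during follow-up after finishing the product.
- **Section 9.11:** align the uses of the ITT and PP sets with the above.
- **Section 9.9:** state that last observation carried forward does not apply to SBI counts or follow-up time. The present rule covers all missing data and has no sensible meaning for either.

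The cost is wording only. Infections and adverse events are already recorded for every treated patient through the visits and the diary (Table 4.2.1), so no extra patients or data are needed. The observed SBI rate may come out slightly less favourable.

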8 SAFETY ASSESSMENT

8.1 Definitions for safety assessment

Adverse event

Adverse event (AE) is any untoward medical occurrence in a study subject, which is not necessarily related to the use of the medicinal product. An adverse event may be any undesirable and unexpected manifestation (including changes in laboratory findings), a symptom or a disease that occurs in temporal association with the administration of the medicinal product (to the study

subject), regardless of whether it is related to the administration of the medicinal product (to the study subject) or not;

Any medical condition that is present at the time of patient's screening, but does not worsen during the study, must not be registered as an AE. However, in case of deterioration of this medical condition at any time during the study, it shall be registered as an AE.

Medical interventions, such as surgeries, diagnostic and therapeutic procedures, are not AEs; however, they are measures undertaken to treat the respective medical condition, and may therefore be registered as AE treatment, unless they are elective.

Deviation of laboratory findings from normal

Any deviation of a laboratory finding from normal, which has appeared for the first time or the severity or frequency of which has increased compared to baseline, and which meets at least one of the following criteria, shall be recorded as an AE:

- Requires a therapeutic intervention or a diagnostic procedure;
- Leads to discontinuation of the IMP;
- Is accompanied by complaints or symptoms, or causes them;
- Is assessed by the investigator as "clinically significant".

In any doubt as to whether the observed clinical event is an AE, the same shall be registered as an AE.

Adverse reaction

Adverse reaction (AR) within a clinical trial of a medicinal product (original/generic) or its evaluation for new use, especially if the therapeutic doses of the medicinal product have not been established, adverse reactions to a medicinal product must encompass all adverse and unpredictable responses to administration of any dose of the medicinal product. The term "response to administration of the medicinal product" implies that there is at least an assumed probability of a causal relationship between the administration of the medicinal product and the adverse reaction, i.e. the correlation cannot be ruled out.

During the study period, the Investigator or study personnel shall survey and document information on cases of adverse events/reactions according to definitions given in this Section of the Protocol.

Unexpected adverse reaction

Unexpected adverse reaction means an adverse reaction the nature or severity of which is not consistent with the available information on the medicinal product (for instance, with the Investigator's Brochure for a non-marketed medicinal product or with the Instruction for Medical Use/Summary of Product Characteristics for a marketed medicinal product);

Serious adverse reaction/Serious adverse event

Serious adverse reaction (SAR) or Serious adverse event (SAE) means any untoward medical occurrence while using the medicinal product (regardless of dosing) leading to death; being life-threatening; requiring hospitalisation or extension of an existing hospitalisation; leading to prolonged or significant incapacitation or disability, congenital abnormalities or birth defects.

Death is usually a result of underlying clinical phenomenon that causes it. Therefore, the cause of death shall be considered as serious AE. The only exception is a "sudden death" when its causes have not been established. In this case, "sudden death" shall be viewed as an AE; the cause of its "seriousness" is its "lethality".

Life threatening: the term "life threatening" (event) is defined as an AE, during the existence of which there was a threat to a patient's life. This does not mean any AE that could hypothetically lead to death if it were more severe.

Hospitalisation: any adverse event leading to hospitalisation or extended hospitalisation will automatically be considered serious if it does not meet any of the non-inclusion criteria listed below:

the hospitalisation lasts less than 12 hours

or

the hospitalisation is planned in advance (i.e. it is an optional or elective surgery, which was agreed upon before the start of this study).

Disability is defined as a significant impairment of a person's ability to perform daily functions, e.g. a congenital anomaly/developmental defect.

8.2 AE detection and documentation

The identification and registration of AEs begins from the time of signing the informed consent and continues until the end of the given patient's participation in the study.

AE identification and registration starts from the moment of drug administration and continues until the end of the patient's participation in the study.

The AEs that occur between the screening and drug administration and that are not SAEs must be recorded as medical history.

All AEs occurring from the moment of drug administration, which are reported by the patient or identified during the follow-up, physical examination and other diagnostic procedures, shall be registered in the AE Report Form, which is a structural constituent of the eCRF.

Laboratory findings will be evaluated during screening and throughout the study.

Information on any AEs observed during the study period, starting with the first administration of the investigational product and up to the end of investigational product use is documented in medical records/outpatient card of the patient and under the AE section in the eCRF. All AEs must be documented, regardless of their severity or causality with the investigational medicinal product.

The following events **must** be classified as AEs:

- exacerbations/flare of pre-existing conditions;
- increase in incidence or severity (intensity) of diseases or previously observed episodic events;
- any disease(s) detected or diagnosed after the onset of treatment with the investigational medicinal product, even if it was possible for the disease(s) to be present before the start of patient's participation in the study;
- any prolonged and/or persistent illnesses or symptoms present at baseline, the severity of which increased after the patient joined the study;
- new signs or any increase in severity of signs and symptoms of diabetes that required immediate treatment, hospitalisation, surgery and/or any other intervention;
- any clinically significant abnormalities of laboratory results or findings of other tests occurring after the onset of treatment with the investigational product, or any such baseline abnormalities, the severity of which increased in a setting of treatment with the investigational medicinal product.

The following events **shall NOT** be classified as AEs:

1. any diseases or abnormalities, which were detected or diagnosed before the start of treatment with the investigational medicinal product, the severity of which does not increase;
2. situations where no adverse medical occurrence is present (e.g. hospitalisation for an elective surgery);

3. overdose of any investigational medicinal product(s) or concomitant medicinal product(s) without any adverse signs or symptoms;
4. any clinically significant laboratory abnormality detected before first dose of the investigational product;
5. signs and symptoms observed during the study that are associated with lack of adequate response to treatment.
6. Death occurring under force majeure circumstances (as defined by Ukrainian law)

The emergence of any adverse events (AEs) will be tracked during the study. Table 8.2.1 presents the treatment tolerability scale.

Table 8.2.1. Treatment tolerability scale

Category	Category description
Good	An objective overview over time shows no abnormal changes or clinically significant deviations, data of the laboratory examination do not change significantly and remain within the normal; the patient does not report any manifestations of adverse reactions
Satisfactory	An objective overview over time shows minor transitory changes that require no modifications in the treatment schedule or additional medical interventions and/or laboratory examination data are insignificantly outside normal limits and/or insignificant adverse reactions are observed that do not cause serious problems for the patient and do not require discontinuation of the product
Unsatisfactory	An objective review over time shows abnormal changes that require discontinuation of the drug and additional medical interventions and/or laboratory findings are subject to clinically significant adverse changes, entailing the need for additional examinations and interpretation of data and/or there is an adverse side reaction that has a significant negative effect on the patient's condition and requires the discontinuation of the product and additional medical interventions

Signs and symptoms underlain by general disease shall, if possible, be indicated as a single complex event. If the diagnosis is known, it must be registered as the name of the AE. If the diagnosis is not known, each complaint and symptom must be registered as a separate AE.

Information to be recorded includes the event type, AE onset date, investigator's assessment of AE severity and AE association with the IMP, AE cessation (resolution) date, AE seriousness, measures taken, and AE outcome.

All AEs shall be monitored until they are adequately resolved.

During and after the subject's participation in the study, the investigator (medical institution) must ensure that the subject is provided with necessary medical care in case of any study-related adverse events, including clinically significant changes in laboratory findings. The Investigator (medical institution) must inform the study subject about any concurrent diseases requiring medical attention, which have become known to the Investigator.

Assessment of AE severity

AE severity (intensity) indicates the extent to which the AE affects the patient's daily activity. AE severity degree will be determined according to NCI CTCAE criteria developed by the US National Cancer Institute (version 5.0) (in each item, a semicolon means "or") Table 8.2.2.

Table 8.2.2. AE severity degree according to NCI CTCAE (version 5.0)

Severity degree 1	Mild; no symptoms or minor symptoms; only clinical or diagnostic observations; no intervention is required
Severity degree 2	Moderate; requires minimal, local or non-invasive intervention (e.g., tamponade, cauterisation); restriction corresponds to Instrumental Activities of Daily Living (ADL*)
Severity degree 3	Severe or clinically significant but not life-threatening; hospitalisation or continuation of hospitalisation is required; restriction in Self Care Activities of Daily Living (ADL**)
Severity degree 4	Life-threatening condition; immediate intervention is required
Severity degree 5	Death associated with AE

Activities of Daily Living (ADL):

*Instrumental Activities of Daily Living include cooking, buying food or clothing, using the phone, handling money, etc.

**Self Care Activities of Daily Living include taking a bath, dressing and undressing, eating independently, using the toilet, taking medication and not being bedridden.

The terms "serious" and "severe" are not synonymous. A severe AE (3rd or 4th severity degree) must not always be considered serious. For example, a white blood cell count of 1000 to 2000 / mm³ shall be considered a degree 3 (severe) AE, but such an AE may not be recognised as serious. A benchmark for submitting information to regulatory authorities is the seriousness (but not severity) of an AE.

Assessment of causal relationship between the AE and the investigational product

During the assessment of causal relationship, the Investigator must take into account the possible aetiology of the observed AE/AR, which may be related to the administration of the investigational medicinal product, concomitant medications, the course of the underlying disease, comorbidities, procedures performed during the study, and other causes. Of all the possible causes, the Investigator must identify the single cause with the likeliest causality to the event in question. During assessment of causality in case of a serious AE, the report shall provide the rationale for the Investigator's judgement. This rationale has to include all of the available facts supporting the judgement, including laboratory results and other diagnostic findings.

- **Verified causality.** The clinical event and/or changes in laboratory results have temporal connection with the use of the medicinal product and cannot be attributed to a comorbidity or to other medicinal products or chemical substances. The response to product discontinuation must be clinically significant. If necessary, the event has been confirmed by a rechallenge.
- **Probable causality.** The clinical event and/or changes in laboratory results have temporal connection with the use of the medicinal product and are unlikely to be attributed to a comorbidity or to other medicinal products or chemical substances and a clinically distinctive response to discontinuation of the product has been observed.
- **Possible causality.** The clinical event and/or changes in laboratory results have temporal connection with the use of the medicinal product, but they are also attributable to existing comorbidities or to other medicinal products or chemical substances. The results of rechallenge may be negative or ambiguous.
- **Dubious causality.** The clinical event and/or changes in laboratory results may have temporal connection with the use of the medicinal product, but other medicinal products, chemical substances or comorbidities are a more likely explanation for the event.

- **No causality.** The clinical event and/or changes in laboratory results are *beyond any reasonable doubt* unrelated to the use of the product in question due to lack of substantiated temporal connection between the drug and the AE and/or implausibility of such a connection.

Categories of AE outcomes and their definitions

The event ended without sequelae: the symptoms are absent and the patient does not require treatment to reverse the AE in question.

Stabilised condition: the outcome of an AE has been evaluated as stable condition, per Investigator's judgement.

The event ended with sequelae: the event was managed successfully, but with sequelae; as a result of the AE, the patient became temporarily or permanently disabled/unable to work; any AE that ended with sequelae is classified as a serious AE.

The event is ongoing: the associated symptoms remain.

Death of the patient.

Result is unknown.

For each AE, actions that were undertaken to improve the patient's general condition must be recorded, namely:

- No treatment;
- Discontinuation of suspected medicinal product;
- Dose reduction of suspected medicinal product;
- Discontinuation of concomitant treatment;
- Use of pharmacological therapy;
- Non-pharmacological therapy (including surgery).

